Grade 1	** (**)
Grade 2	** (**)
Grade 3	** (**)
Grade 4	** (**)
Alkaline phosphatase	
Grade 1	** (**)
Grade 2	** (**)
Grade 3	** (**)
Grade 4	** (**)
ALT	
Grade 1	** (**)
Grade 2	** (**)
Grade 3	** (**)
Grade 4	** (**)
AST	
Grade 1	** (**)
Grade 2	** (**)
Grade 3	** (**)
Grade 4	** (**)
LDH	
Normal	** (**)
High ⁽¹⁾	** (**)
Serum Creatinine	
Grade 1	** (**)
Grade 2	** (**)
Grade 3	** (**)
Grade 4	** (**)
Hypernatremia	
Grade 1	** (**)
Grade 2	** (**)
Grade 3	** (**)
Grade 4	** (**)
Hyponatremia	** (**)
Grade 1	** (**)
Grade 2	** (**)
Grade 3	** (**)
Grade 4	** (**)
Hyperkalemia	
Grade 1	** (**)
Grade 2	** (**)
Grade 3	** (**)
Grade 4	** (**)
Hypokalemia	
Grade 1	** (**)
Grade 2	** (**)
Grade 3	** (**)

Grade 4	** (**)
Hypercalcemia	
Grade 1	** (**)
Grade 2	** (**)
Grade 3	** (**)
Grade 4	** (**)
Hypocalcemia	
Grade 1	** (**)
Grade 2	** (**)
Grade 3	** (**)
Grade 4	** (**)
Hypermagnesemia	
Grade 1	** (**)
Grade 2	** (**)
Grade 3	** (**)
Grade 4	** (**)
Hypomagnesemia	
Grade 1	** (**)
Grade 2	** (**)
Grade 3	** (**)
Grade 4	** (**)
Hyperalbuminemia	
Grade 1	** (**)
Grade 2	** (**)
Grade 3	** (**)
Grade 4	** (**)
Hypoalbuminemia	
Grade 1	** (**)
Grade 2	** (**)
Grade 3	** (**)
Grade 4	** (**)
Chloride	
Normal	** (**)
High ⁽¹⁾	** (**)
ALP	
Grade 1	** (**)
Grade 2	** (**)
Grade 3	** (**)
Grade 4	** (**)
Amylase	
Grade 1	** (**)
Grade 2	** (**)
Grade 3	** (**)
Grade 4	** (**)
Lipase	
Grade 1	** (**)
Grade 2	** (**)
Grade 3	** (**)
Grade 4	** (**)
CEA	
Normal	** (**)
High ⁽¹⁾	** (**)

⁽¹⁾ Greater than upper normal limit

Table 50: Overall Serum Chemistry: Worst Grade per Patient

Data set: All Treated Patients		
	Number of Patients (%)	
	DURVA+TREME N = ***	BSC N = ***
Total bilirubin		
Grade 1	** (**)	** (**)
Grade 2	** (**)	** (**)
Grade 3	** (**)	** (**)
Grade 4	** (**)	** (**)
Alkaline phosphatase		
Grade 1	** (**)	** (**)
Grade 2	** (**)	** (**)
Grade 3	** (**)	** (**)
Grade 4	** (**)	** (**)
ALT		
Grade 1	** (**)	** (**)
Grade 2	** (**)	** (**)
Grade 3	** (**)	** (**)
Grade 4	** (**)	** (**)
AST		
Grade 1	** (**)	** (**)
Grade 2	** (**)	** (**)
Grade 3	** (**)	** (**)
Grade 4	** (**)	** (**)
LDH		
Normal	** (**)	** (**)
High ⁽¹⁾	** (**)	** (**)
Serum Creatinine		
Grade 1	** (**)	** (**)
Grade 2	** (**)	** (**)
Grade 3	** (**)	** (**)
Grade 4	** (**)	** (**)
Hypernatremia		
Grade 1	** (**)	** (**)
Grade 2	** (**)	** (**)
Grade 3	** (**)	** (**)
Grade 4	** (**)	** (**)
Hyponatremia		
Grade 1	** (**)	** (**)
Grade 2	** (**)	** (**)
Grade 3	** (**)	** (**)
Grade 4	** (**)	** (**)
Hyperkalemia		
Grade 1	** (**)	** (**)
Grade 2	** (**)	** (**)
Grade 3	** (**)	** (**)
Grade 4	** (**)	** (**)
Hypokalemia		
Grade 1	** (**)	** (**)
Grade 2	** (**)	** (**)
Grade 3	** (**)	** (**)
Grade 4	** (**)	** (**)

Hypercalcemia		
Grade 1	** (**)	** (**)
Grade 2	** (**)	** (**)
Grade 3	** (**)	** (**)
Grade 4	** (**)	** (**)
Hypocalcemia		
Grade 1	** (**)	** (**)
Grade 2	** (**)	** (**)
Grade 3	** (**)	** (**)
Grade 4	** (**)	** (**)
Hypermagnesemia		
Grade 1	** (**)	** (**)
Grade 2	** (**)	** (**)
Grade 3	** (**)	** (**)
Grade 4	** (**)	** (**)
Hypomagnesemia		
Grade 1	** (**)	** (**)
Grade 2	** (**)	** (**)
Grade 3	** (**)	** (**)
Grade 4	** (**)	** (**)
Hyperalbuminemia		
Grade 1	** (**)	** (**)
Grade 2	** (**)	** (**)
Grade 3	** (**)	** (**)
Grade 4	** (**)	** (**)
Hypoalbuminemia		
Grade 1	** (**)	** (**)
Grade 2	** (**)	** (**)
Grade 3	** (**)	** (**)
Grade 4	** (**)	** (**)
Chloride		
Normal	** (**)	** (**)
High ⁽¹⁾	** (**)	** (**)
Amylase		
Grade 1	** (**)	** (**)
Grade 2	** (**)	** (**)
Grade 3	** (**)	** (**)
Grade 4	** (**)	** (**)
Lipase		
Grade 1	** (**)	** (**)
Grade 2	** (**)	** (**)
Grade 3	** (**)	** (**)
Grade 4	** (**)	** (**)
CEA		
Normal	** (**)	** (**)
High ⁽¹⁾	** (**)	** (**)

⁽¹⁾ Greater than upper normal limit

Table 51: Thyroid Function Tests: Worst during Durvalumab and Tremelimumab Treatment

Data set: All Treated Patients on DURVA+TREME Arm	
	Number of Patients (%)
	DURVA+TREME N = ***
TSH	
Normal	** (**)
<1-0.5xLLN	** (**)
<0.5-0.1xLLN	** (**)
<0.1xLLN	
T3 Free	** (**)
Normal	** (**)
<1-0.5xLLN	** (**)
<0.5-0.1xLLN	** (**)
<0.1xLLN	** (**)
T3 Total	
Normal	** (**)
<1-0.5xLLN	** (**)
<0.5-0.1xLLN	** (**)
<0.1xLLN	** (**)
T4 Free	
Normal	** (**)
<1-0.5xLLN	** (**)
<0.5-0.1xLLN	** (**)
<0.1xLLN	** (**)
T4 Total	
Normal	** (**)
<1-0.5xLLN	** (**)
<0.5-0.1xLLN	** (**)
<0.1xLLN	** (**)

Table 52: Thyroid Function Tests: Worst during Study

Data set: All Treated Patients		
	Number of Patients (%)	
	DURVA+TREME N = ***	BSC N = ***
TSH		
Normal	** (**)	** (**)
<1-0.5xLLN	** (**)	** (**)
<0.5-0.1xLLN	** (**)	** (**)
<0.1xLLN	** (**)	** (**)
T3 Free		
Normal	** (**)	** (**)
<1-0.5xLLN	** (**)	** (**)
<0.5-0.1xLLN	** (**)	** (**)
<0.1xLLN	** (**)	** (**)
T3 Total		
Normal	** (**)	** (**)
<1-0.5xLLN	** (**)	** (**)
<0.5-0.1xLLN	** (**)	** (**)

T4 Free	<0.1xLLN	** (**)	** (**)
	Normal	** (**)	** (**)
	<1-0.5xLLN	** (**)	** (**)
	<0.5-0.1xLLN	** (**)	** (**)
	<0.1xLLN	** (**)	** (**)
T4 Total			
	Normal	** (**)	** (**)
	<1-0.5xLLN	** (**)	** (**)
	<0.5-0.1xLLN	** (**)	** (**)
	<0.1xLLN	** (**)	** (**)

Table 53: Coagulation Tests: Worst during Durvalumab and Tremelimumab Treatment

Data set: All Treated Patients on DURVA+TREME		Number of Patients (%)	
		DURVA+TREME N = ***	
PT	Grade 1	** (**)	
	Grade 2	** (**)	
	Grade 3	** (**)	
	Grade 4	** (**)	
INR	Grade 1	** (**)	
	Grade 2	** (**)	
	Grade 3	** (**)	
	Grade 4	** (**)	
PTT	Grade 1	** (**)	
	Grade 2	** (**)	
	Grade 3	** (**)	
	Grade 4	** (**)	

Table 54: Coagulation Tests: Worst during Study

Data set: All Treated Patients		Number of Patients (%)	
		DURVA+TREME N = ***	BSC N = ***
PT	Grade 1	** (**)	** (**)
	Grade 2	** (**)	** (**)
	Grade 3	** (**)	** (**)
	Grade 4	** (**)	** (**)
INR	Grade 1	** (**)	** (**)
	Grade 2	** (**)	** (**)
	Grade 3	** (**)	** (**)
	Grade 4	** (**)	** (**)
PTT	Grade 1	** (**)	** (**)
	Grade 2	** (**)	** (**)
	Grade 3	** (**)	** (**)
	Grade 4	** (**)	** (**)

Table 55: ECG Results

Data set: All Treated Patients		
	Number of patients (%)	
	DURVA+TREME N=***	BSC N=***
ECG reported	*** (**)	*** (**)
All Normal	**	**
At least one abnormal but none clinically important	**	**
At least one abnormal and clinically important		
ECG not reported/not performed	*** (**)	*** (**)

Table 56 : Urinalysis

Data set: All Treated Patients		
	Number of patients (%)	
	ARM A N = **	ARM B N = **
Urinalysis – SPOT Test		
Negative/trace	** (**)	** (**)
1+(>20 mg/dL–30 mg/dL)	** (**)	** (**)
2+(>30 mg/dL–100 mg/dL)	** (**)	** (**)
3+(>100 mg/dL– 300 mg/dL)	** (**)	** (**)
4+(>300 mg/dL)	** (**)	** (**)
Urinalysis – 24-Hour Test (g/day)		
Grade		
1	** (**)	** (**)
2	** (**)	** (**)
3	** (**)	** (**)

Table 57: Deaths During Durvalumab and Tremelimumab Treatment or within 4 weeks of Last Durvalumab and Tremelimumab Treatment

Data set: All Treated Patients on DURVA+TREME Arm	
	Number of Patients (%)
	DURVA+TREME N=***
Number of Patients who died during or within 4 weeks of last Durvalumab and Tremelimumab treatment	** (**)
Cause of Death	
Colorectal cancer	**
Toxicity from protocol treatment	**
Colorectal cancer + Toxicity from protocol treatment complication	**
Non-protocol Treatment Complication	**
Colorectal cancer + Non-protocol Treatment Complication	**
Other Primary Malignancy	**
Other Condition or Circumstance	**

Table 58: Adverse Event leading to Discontinuation of Durvalumab or Tremelimumab^(a)

Data set: All Treated Patients on DURVA+TREME Arm	
	Number of patients (%)
	DURVA+TREME N=***
Number discontinued durvalumab from adverse events	** (**)
<Adverse event 1>	**
<Adverse event 2>	**
....	
Number discontinued Tremelimumab from adverse events	** (**)
<Adverse event 1>	**
<Adverse event 2>	**
....	

(a) From End of Treatment Form with off reasons= "Adverse events related to protocol therapy".

Table 59: Concomitant Medications

Data set: All Treated Patients		
	Number of patients (%)	
	DURVA+TREME N = ***	BSC N=***
Any concomitant medication during or 4 weeks after Durvalumab and Tremelimumab Treatment for patients on DURVA+TREME and before objective progression on BSC		
No	** (**)	** (**)
Yes	** (**)	** (**)
Type of concomitant medications ⁽¹⁾		
Medication A	** (**)	** (**)
...		

(1): patients may have received more than one concomitant medication.

Table 60: Anti-Cancer Treatment

	Number of patients (%)	
	DURVA+TREME N=***	BSC N=***
Number of patients with any anti-cancer treatment during or 4 weeks after Durvalumab and Tremelimumab Treatment	*** (**)	NAP (NAP)
Chemotherapy ⁽¹⁾	*** (**)	NAP (NAP)
Drug 1 ...	*** (**)	NAP (NAP)
Radiotherapy ⁽¹⁾	*** (**)	NAP (NAP)
Hormonal therapy ⁽¹⁾	*** (**)	NAP (NAP)
Drug 1 ...	*** (**)	NAP (NAP)
Immunotherapy ⁽¹⁾	*** (**)	NAP (NAP)
Drug 1 ...	*** (**)	NAP (NAP)
Other ⁽¹⁾	*** (**)	NAP (NAP)
Drug 1 ...	*** (**)	NAP (NAP)
Number of patients with any anti-cancer treatment before progression	*** (**)	*** (**)
Chemotherapy ⁽¹⁾	*** (**)	*** (**)
Drug 1 ...	*** (**)	*** (**)
Radiotherapy ⁽¹⁾	*** (**)	*** (**)
Hormonal therapy ⁽¹⁾	*** (**)	*** (**)
Drug 1 ...	*** (**)	*** (**)
Immunotherapy ⁽¹⁾	*** (**)	*** (**)
Drug 1 ...	*** (**)	*** (**)
Other ⁽¹⁾	*** (**)	*** (**)
Drug 1 ...	*** (**)	*** (**)
Number of patients with any anti-cancer treatment after progression	*** (**)	*** (**)
Chemotherapy ⁽¹⁾	*** (**)	*** (**)
Drug 1 ...	*** (**)	*** (**)
Radiotherapy ⁽¹⁾	*** (**)	*** (**)
Hormonal therapy ⁽¹⁾	*** (**)	*** (**)
Drug 1 ...	*** (**)	*** (**)
Immunotherapy ⁽¹⁾	*** (**)	*** (**)
Drug 1 ...	*** (**)	*** (**)
Other ⁽¹⁾	*** (**)	*** (**)
Drug 1 ...	*** (**)	*** (**)

(1) Patients could have more than one type of anti-cancer treatment. NA=Not applicable.

Table 61: Major Medical Problems

Data set: All Treated Patients		
	Number of patients (%)	
	DURVA+TREME N = ***	BSC N=***
Any major medical problem during or 4 weeks after Durvalumab and Tremelimumab Treatment for patients on DURVA+TREME and before objective progression on BSC		
No	** (**)	** (**)
Yes	** (**)	** (**)
Type of major medical problems ⁽¹⁾		
Medication A	** (**)	** (**)
...		

(1): patients may have more than one major medical problem.

Table 62: Compliance Rate with QoL Assessment by Treatment Arm

	DURVA+TREME		BSC	
	Expected	Received (%)	Expected	Received (%)
Baseline	***	** (**)	***	** (**)
4 weeks	***	** (**)	***	** (**)
8 weeks	***	** (**)	***	** (**)
12 weeks	***	** (**)	***	** (**)
16 weeks	***	** (**)	***	** (**)
24 weeks	***	** (**)	***	** (**)

Table 63: Proportion of Patients with Deterioration, Improvement or Stable QoL

	N	DURVA+TREME N (%)	BSC N (%)	P value*
Deterioration				
Physical function				0.***
Week 8	***	*** (** **)	*** (** **)	
Week 16	***	*** (** **)	*** (** **)	
Global health status				0.***
Week 8	***	*** (** **)	*** (** **)	
Week 16	***	*** (** **)	*** (** **)	
Improvement				
Physical function				0.***
Week 8	***	*** (** **)	*** (** **)	
Week 16	***	*** (** **)	*** (** **)	
Global health status				0.***
Week 8	***	*** (** **)	*** (** **)	
Week 16	***	*** (** **)	*** (** **)	
Stable				
Physical function				0.***
Week 8	***	*** (** **)	*** (** **)	
Week 16	***	*** (** **)	*** (** **)	
Global health status				0.***
Week 8	***	*** (** **)	*** (** **)	
Week 16	***	*** (** **)	*** (** **)	

* Fisher's exact test

Table 64: Time to Deterioration in QoL Primary Endpoints

Data set: All patients who had baseline and at least one follow-up QoL assessment				
	DURVA+TREME		BSC	
	N	Median (months) (90% CI)	N	Median (months) (90% CI)
Physical function	***	** ** (** **, ** **)	***	** ** (** **, ** **)
Global Health Scale	***	** ** (** **, ** **)	***	** ** (** **, ** **)

Table 65: QoL: Summary Baseline Scores

	DURVA+TREME	BSC	P value*
Functional scales			
Physical			0.***
N	***	***	
Mean	***	***	
STD	***	***	
...	
Global health status			0.***
N	***	***	
Mean	***	***	
STD	***	***	
Symptom scales			
Fatigue			0.***
N	***	***	
Mean	***	***	
STD	***	***	
...	

* Wilcoxon rank sum test

Table 66: Summary QOL Change Scores from Baseline for Scale/Domain/Item at Each Time Period*

	DURVA+TREME	BSC	P Value**
Scale/Domain/Item			
Week 4			**
N	***	***	
Mean	***	***	
STD	***	***	
Week 8			**
N			
Mean	***	***	
STD	***	***	
Week 12			**
N			
Mean	***	***	
STD	***	***	
Week 16			**
N			
Mean	***	***	
STD	***	***	
Week 24			**
N			
Mean	***	***	
STD	***	***	

* Table will be provided for each scale/domain/item.

** Wilcoxon rank sum test

Table 67: Results for QOL Response Analyses

Domain	DURVA+TREME			BSC			P-value*
	Improved	Stable N (%)	Worsened	Improved	Stable N (%)	Worsened	
EORTC QLQ-C30							
Physical	***(**)	***(**)	***(**)	***(**)	***(**)	***(**)	.**
Role	***(**)	***(**)	***(**)	***(**)	***(**)	***(**)	.**
Emotional	***(**)	***(**)	***(**)	***(**)	***(**)	***(**)	.**
Cognitive	***(**)	***(**)	***(**)	***(**)	***(**)	***(**)	.**
Social	***(**)	***(**)	***(**)	***(**)	***(**)	***(**)	.**
Global	***(**)	***(**)	***(**)	***(**)	***(**)	***(**)	.**
Pain	***(**)	***(**)	***(**)	***(**)	***(**)	***(**)	.**
Fatigue	***(**)	***(**)	***(**)	***(**)	***(**)	***(**)	.**
Nausea	***(**)	***(**)	***(**)	***(**)	***(**)	***(**)	.**
Dyspnea	***(**)	***(**)	***(**)	***(**)	***(**)	***(**)	.**
Sleep	***(**)	***(**)	***(**)	***(**)	***(**)	***(**)	.**
Appetite	***(**)	***(**)	***(**)	***(**)	***(**)	***(**)	.**
Constipation	***(**)	***(**)	***(**)	***(**)	***(**)	***(**)	.**
Diarrhea	***(**)	***(**)	***(**)	***(**)	***(**)	***(**)	.**
Financial	***(**)	***(**)	***(**)	***(**)	***(**)	***(**)	.**

* Chi-square test

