13.3 Sample Size and Duration of Study

The study is designed to have a power of 80% and a two-sided alpha of 10% to detect a 35% reduction in the continuous risk of death (HR 0.65, which corresponds to an increase of median survival from 4.5 to 6.9 months). It is estimated that 150 events will be required to detect this reduction. The final analysis will be performed when 150 events are observed. Assuming an accrual rate of around 10 patients per month, the required number of events would be observed by accruing a total of 180 patients and following them for a minimum of 6 months. The total duration of the trial would be around 24 months.

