7.6 Efficacy

7.6.1 Overall survival

For all randomized patients, survival is calculated from the day of randomization (as recorded in Centralized Randomization File) to death (Date/Cause of Death Section of Death Report). For alive patients, survival is censored at the last day the patient is known alive (LKA) as the last recorded date known alive (Date of Attendance/Last Contact on Best Support Care Report, 4-Week Post Treatment Report, Follow-up Report, Short Follow Up Report, and Minimal Follow-up Report; or last date of infusion of durvalumab or tremelimumab in Treatment Report). Survival time (in months) is defined as

$$[(\text{date of death or LKA} - \text{date of randomization}) + 1]/30.4375.$$

A frequency table for the number of patients who died and cause of death in each treatment arm will be provided (**Table 32**). Kaplan-Meier curve for proportions of survival in each treatment arm will be displayed (**Figure 2**).

The comparison of overall survival between the two treatment arms is the primary objective of this study. The primary analysis will be the log-rank test (**Table 33**) stratified by the factors coded as:

Stratification Factors (at randomization)

Performance status	1 = ECOG 0	0 = ECOG 1
Site of tumour	1=right colon; 2=transverse colon; 3=left colon; 4=rectum; 5=unknown	

The hazard ratio of durvalumab and tremelimumab combined with best supportive care (ARM 2) over best supportive care alone (ARM 1) and two-sided 90% CI will be calculated (**Table 33**) based on the Cox regression model stratified by above stratification factors, and with treatment arm coded as ARM 2=1 and ARM 1=0. The 90% confidence intervals for the median survival will be computed using the method of Brookmeyer and Crowley [2].

In order to assess the influence of the potential prognostic factors shown and coded below on the comparison of survival between treatment arms, a stratified Cox regression model will be used with all variables (treatment arm and prognostic factors) included to estimate hazard ratios and 90% confidence intervals (**Table 33**).

Prognostic factors (at baseline)

Gender	0 = Female	1 = Male
Age	0 = ≥ 65	1 = < 65
Number of organ sites	0 = > 2	1 = ≤ 2
Presence of liver metastases	0 = Yes	1 = No

No interactions will be considered in the model.

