7.6.3 Progression-free Survival

Progression-free survival (PFS) will be calculated for all patients from the day of randomization until the first observation of disease progression (date of objective relapse or progression of Relapse/Progression Report) or death due to any cause (recorded in Date/Cause of Death Section of Death Report) as the (difference+1).

If a patient has not progressed or died, PFS will be censored on the date of last disease assessment defined as the earliest test date of target lesion or non-target lesions (if patient has no target lesions), whichever is latest.

A frequency table will be provided describing progression and censoring as follows (**Table 35**):

- Number of patients who progress (documented progression, death without documented progression)
- Number of patients censored (alive and not progressed)

Analyses for PFS will be similar to that for overall survival as previously described. A Kaplan-Meier curve for PFS in each treatment arm will be displayed (**Figure 3**). In the primary analysis, median PFS for the two treatments will be compared using the stratified log-rank test (**Table 36**). A stratified Cox regression model will estimate the durvalumab and tremelimumab combined with best supportive care (ARM 2) over best supportive care alone (ARM 1) PFS hazard ratio and 90% C. I. (**Table 36**). In addition, a stratified Cox regression model adjusted for covariates will be applied to verify the impact of the prognostic factors on the treatment effect (**Table 36**).

Coding for treatment arm, stratification variables and prognostic factors is identical to that presented in **Section 7.5.1**.

Some patients received other anti-cancer therapy before progression or death. Sensitivity analyses will be performed by censoring those who have received anti-cancer therapy prior to documentation of disease relapse/progression or death on the earliest date cancer treatment began or treating them as having PFS events at the earliest date when the treatment began.

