Number of Patients who died	** (**)	** (**)
Cause of Death		
Colorectal cancer only	**	**
Toxicity from protocol treatment	**	**
Colorectal cancer + Toxicity from protocol treatment complication	**	**
Non-protocol Treatment Complication	**	**
Colorectal cancer + Non-protocol Treatment Complication	**	**
Other Primary Malignancy	**	**
Other Condition or Circumstance	**	**

Figure 2: Kaplan-Meier Curves for Overall Survival

Table 33: Log Rank and Cox Regression Model for Overall Survival

Data set: All Randomized Patients						
Treatment Arm/ Prognostic Factors at Baseline	N	Univariate Analysis ⁽¹⁾		Log- rank p-value	Multivariate Analysis ⁽²⁾	
		Median Survival (Months)	Hazard Ratio ⁽⁴⁾ (90% CI)		Hazard Ratio ⁽⁴⁾ (90% C.I.)	P-value from Cox regre- sion
Treatment arm				0.***		0.***
DURVA+TREME	***	**.*	**.*		**.*	
BSC	***	**.*	(**.*; **.*)		(**.*; **.*)	
Gender				0.***		0.***
Male	***	**.*	NC ⁽³⁾		**.*	
Female	***	**.*			(**.*; **.*)	
Age				0.***		0.***
<65	***	**.*	NC		**.*	
≥65	***	**.*			(**.*; **.*)	
Number of organ sites				0.***		0.***
≤ 2	***	**.*	NC		**.*	
>2	***	**.*			(**.*; **.*)	
Presence of liver metastases				0.***		0.***
Yes	***	**.*	NC		**.*	
No	***	**.*			(**.*; **.*)	

(1) Stratified; (2) Stratified Cox regression with all factors included; (3) NC = not computed
(4) Hazard ratio of first category over second category

Table 34: Survival by Subsets

Data set: All Randomized Patients						
Factors	Value	DURVA+TREME		BSC		Hazard Ratio ⁽¹⁾ 90% C.I.
		N	Median Survival 90% C.I.	N	Median Survival 90% C.I.	
Performance Status at baseline	ECOG 0	**	*** (** ***)	**	*** (** ***)	*** (** ***)
	ECOG 1	**	*** (** ***)	**	*** (** ***)	*** (** ***)
Age	<65	**	*** (** ***)	**	*** (** ***)	*** (** ***)
	≥65	**	*** (** ***)	**	*** (** ***)	*** (** ***)
Gender	Female	**	*** (** ***)	**	*** (** ***)	*** (** ***)
	Male	**	*** (** ***)	**	*** (** ***)	*** (** ***)
Race	White	**	*** (** ***)	**	*** (** ***)	*** (** ***)
	Black	**	*** (** ***)	**	*** (** ***)	*** (** ***)
	Other	**	*** (** ***)	**	*** (** ***)	*** (** ***)
Site of tumour	Right colon	**	*** (** ***)	**	*** (** ***)	*** (** ***)
	Transverse colon	**	*** (** ***)	**	*** (** ***)	*** (** ***)
	Left colon	**	*** (** ***)	**	*** (** ***)	*** (** ***)
	Rectum	**	*** (** ***)	**	*** (** ***)	*** (** ***)
KRAS Status	Wildtype	**	*** (** ***)	**	*** (** ***)	*** (** ***)
	Mutated	**	*** (** ***)	**	*** (** ***)	*** (** ***)

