Treatment arm DURVA+TREME: BSC	**.* (**.*; **.*)	0.***	**.* (**.*; **.*)	0.***
Gender Male: Female	NC ⁽³⁾	0.***	**.* (**.*; **.*)	0.***
Age <65: ≥65	NC	0.***	**.* (**.*; **.*)	0.***
Number of organ sites ≤2: >2	NC	0.***	**.* (**.*; **.*)	0.***
Number of previous chemo drug classes ≤2: >2	NC	0.***	**.* (**.*; **.*)	0.***
Presence of liver metastases No: Yes	NC	0.***	**.* (**.*; **.*)	0.***

(1) Stratified

(2) Stratified Logistic regression, all factors included

(3) NC = not computed

(4) Odds ratio of first category over second category

Table 40: Response According to Pretreatment Characteristics

Data set: All Randomized Patients		
	Number of Responses/Number of Patients (%)	
	DURVA+TREME N=***	BSC N=***
Gender		
Male	**/** (**)	**/** (**)
Female	**/** (**)	**/** (**)
Age		
< 65 years	**/** (**)	**/** (**)
≥ 65 years	**/** (**)	**/** (**)
Race		
White	**/** (**)	**/** (**)
Black	**/** (**)	**/** (**)
Other	**/** (**)	**/** (**)
Baseline performance status		
ECOG 0-1	**/** (**)	**/** (**)
ECOG 2	**/** (**)	**/** (**)
Site of Tumour		
Right colon	**/** (**)	**/** (**)
Transverse colon	**/** (**)	**/** (**)
Left colon	**/** (**)	**/** (**)
Rectum	**/** (**)	**/** (**)
KRAS status		
Wildtype	**/** (**)	**/** (**)
Mutated	**/** (**)	**/** (**)
NRAS status		
Wildtype	**/** (**)	**/** (**)
Mutated	**/** (**)	**/** (**)
BRAF status		
Wildtype	**/** (**)	**/** (**)
Mutated	**/** (**)	**/** (**)
MSI status		
MSI-H	**/** (**)	**/** (**)
MSI-L	**/** (**)	**/** (**)
MSS	**/** (**)	**/** (**)

Table 41: Duration of Response

Data set: All Randomized Patients with CR or PR			
	DURVA+TREME N=***	BSC N=***	P-value ⁽¹⁾
Median Duration of Response (months) (90% CI)	*** (**_**)	*** (**_**)	.**

(1) Stratified

Table 42: Adverse Events on Durvalumab and Tremelimumab Treatment

Data set: All Treated Patients on DURVA+TREME Arm							
	Number of patients (%) N=***						
	Worst grade						Any grade
	NR	1	2	3	4	5	
Patients with any AE	** (**)	** (**)	** (**)	** (**)	** (**)	** (**)	** (**)
Patients with AE within category							
Category 1 ⁽¹⁾	** (**)	** (**)	** (**)	** (**)	** (**)	** (**)	** (**)
Event 1	** (**)	** (**)	** (**)	** (**)	** (**)	** (**)	** (**)
Event 2	** (**)	** (**)	** (**)	** (**)	** (**)	** (**)	** (**)
Event 3	** (**)	** (**)	** (**)	** (**)	** (**)	** (**)	** (**)
...							

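### SAP Tables 33 and 36 label the liver-metastasis hazard ratio as Yes over No, but the coding in SAP 7.6.1 makes the model return No over Yes

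*SAP*

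**What the plan says.** SAP 7.6.1 sets out the adjusted analysis of overall survival: "a stratified Cox regression model will be used with all variables (treatment arm and prognostic factors) included to estimate hazard ratios and 90% confidence intervals". Treatment enters "with treatment arm coded as ARM 2=1 and ARM 1=0". The prognostic factors are also 0/1 variables, with 1 given to male sex, age below 65 and two or fewer organ sites. The remaining factor is coded "Presence of liver metastases 0 = Yes 1 = No".

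The results go into Table 33. Each factor has two rows with N and median survival. An adjusted hazard ratio with its 90% interval is given per factor, and the footnote on direction reads "4) Hazard ratio of first category over second category". The liver-metastasis rows are Yes, then No.

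Table 36 has the same rows, order and footnote for PFS. A note beneath it says that the table will be repeated for two sensitivity analyses of patients who start other anti-cancer treatment before progression. SAP 7.6.3 carries the coding over: "Coding for treatment arm, stratification variables and prognostic factors is identical to that presented in" an earlier section, given as 7.5.1. Table 39, for objective response, shows the same factor in the other order: "Presence of liver metastases No: Yes".

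**The concern.** With a 0/1 covariate, the exponentiated Cox coefficient is the hazard at level 1 over the hazard at level 0. For the other factors the level coded 1 is also the first row, so the model output can go straight into the shell and the footnote is true. For liver metastases the level coded 1 is the second row. An analyst who fills that cell in the same way as the others would report No over Yes under a label that says Yes over No.

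What is at stake is the stated direction of one prespecified prognostic factor. If liver metastases shorten survival, the unconverted entry would show a ratio below 1 against the Yes category. The p-value would give no warning, because it is the same in both directions.

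**Working it through.** **Whether the plan has a figure to reproduce.** It gives none for this factor. Its one related figure is the design event count in Protocol 13.3 ("power of 80% and a two-sided alpha of 10% to detect a 35% reduction in the continuous risk of death (HR 0.65"). With 2:1 allocation this is (1.645 + 0.842)² / [(2/3)(1/3)(ln 0.65)²] = 6.18 / (0.2222 × 0.1856) ≈ 150 deaths, which agrees with the protocol. The point here does not depend on it.

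**Step 1. Coding against row order.** Inputs are the coding in SAP 7.6.1 and the layouts of Tables 33, 36 and 39.

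| Factor | Coded 1 (7.6.1) | First in Tables 33 and 36 | First in Table 39 | Tables 33 and 36 agree with coding? |
|---|---|---|---|---|
| Treatment | Arm 2 | Durva+Treme | Durva+Treme | Yes |
| Sex | Male | Male | Male | Yes |
| Age | < 65 | < 65 | < 65 | Yes |
| Organ sites | ≤ 2 | ≤ 2 | ≤ 2 | Yes |
| Liver metastases | No | Yes | No | No |

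Four of five rows agree in Tables 33 and 36. In Table 39 all five agree with the coding.

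**Step 2. What the model returns.** Let x = 1 for No and 0 for Yes, with coefficient β. Within each stratum the hazard is h₀(t)·exp(… + βx), so exp(β) = HR(No/Yes). The footnote with rows Yes, No asks for HR(Yes/No) = exp(−β) = 1/exp(β). The 90% limits for No/Yes are exp(β ± 1.645·SE). Those for Yes/No are their reciprocals with lower and upper swapped.

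**Step 3. What does not change.** Put x′ = 1 − x. Then βx = β − βx′, and the constant β is absorbed into the baseline hazard. The liver coefficient changes sign, its standard error and p-value stay the same, and every other coefficient, including treatment, is unchanged. The stratified log-rank test and the Kaplan-Meier medians do not use this coding.

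**Step 4. Size.** The documents give no effect size for liver metastases, so these values are assumed:

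- true Yes/No 1.25: unconverted entry 1/1.25 = 0.80
- true Yes/No 1.5: unconverted entry 1/1.5 = 0.67
- true Yes/No 2.0: unconverted entry 1/2.0 = 0.50

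**Step 5. Numerical illustration.** A stratified Cox model was fitted to one simulated data set of 180 patients with 2:1 allocation, an assumed 70% with liver metastases, an assumed true Yes/No ratio of 1.5, and a simplified two-level stratum. These are not trial data.

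| Liver coding | Liver HR (90% CI) | p | Treatment HR |
|---|---|---|---|
| As in 7.6.1 (No = 1) | 0.694 (0.511 to 0.942) | 0.049 | 0.619 |
| As the footnote labels it (Yes = 1) | 1.441 (1.062 to 1.956) | 0.049 | 0.619 |

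Check: 1/0.6939 = 1.441, 1/0.9417 = 1.062 and 1/0.5112 = 1.956.

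**Step 6. Where it can appear.** Only the adjusted column is exposed, because the univariate hazard ratio for each prognostic factor is marked as not computed. That is one cell in each of four tables: Table 33, Table 36 and the two sensitivity copies of Table 36.

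**The case against.** A reader might infer that the plan directs the liver-metastasis ratio to be printed upside down. It does not. The footnote defines the contrast to be reported, and with Yes listed first it asks for Yes over No. The coding fixes the sign of the coefficient and does not prevent the analyst from reporting its reciprocal. Someone who reads the footnote and converts prints the correct value. That part of the objection stands: the inversion is conditional.

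It is also fair to say that the table offers a partial safeguard. Medians for Yes and No are printed beside the ratio, and a large inversion would probably look odd against them. The safeguard is incomplete, because the medians are unadjusted and a modest effect might not show.

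A reader might further infer that the adjusted treatment comparison is at risk. The algebra in Step 3 rules this out. The stated purpose of the model is to see how prognostic factors bear on the treatment comparison. The liver-metastasis ratio is not an objective or endpoint, and no decision depends on it.

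Last, applying the 7.6.1 coding to Table 36 relies on a cross-reference that points to the wrong place: 7.5.1 describes study therapy and contains no coding. Reading it as 7.6.1 is the sensible interpretation, since that is the only section with such coding, but it remains an inference. None of this removes the disagreement between coding and row order.

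**Conclusion.** The inconsistency is real and confined to one factor. The coding gives No over Yes, and the label in Tables 33 and 36 says Yes over No. If the model output is entered as it stands, one adjusted hazard ratio and its 90% limits are inverted in each of four tables. For a true ratio between 1.25 and 2.0 the printed value would lie between 0.80 and 0.50; that range is an assumption. The conclusion also assumes that the PFS coding is that of 7.6.1. It is a minor reporting error, worth correcting because the plan should not rely on a programmer noticing that one row in five breaks the pattern.

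**What to change.** List No before Yes for liver metastases in Tables 33 and 36. This matches the coding and Table 39, carries through to the two sensitivity versions of Table 36, and changes no model. The alternative is to recode Yes = 1, No = 0 in 7.6.1 and leave Tables 33 and 36 as they are, but Table 39 must then be reversed.

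In the same edit, correct the two coding cross-references: 7.6.3 points to 7.5.1 (study therapy) and 7.6.5 points to 7.4.1 (pretreatment characteristics), and both should point to 7.6.1.

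The preferred option costs one pair of rows in each of two table shells, plus two section numbers. It has no statistical cost.
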